APPENDIX A: SCHEDULE OF EVENTS

		Screening	Baseline	Enrollment/ Randomization	Every cycle ^A						EOT ^B	Time of Transplant	Long-term F/U Months after ASCT or EOT						
					D1 (±1d)	D2 ^V	D4 ^V	D8 (±1d)	D15 (±1d)	D22 ^W (±3d)	14–30 days post start of last cycle		3	6	12	18	24	>24	
Visit Window		D –28 to 1	D –7 to 1										±1 month					Annually ±1 mo	
Screening/ Baseline Assessments	Informed consent	X		Eligibility documentation submitted to Sponsor prior to randomization															
	Inclusion/exclusion	X																	
	Medical history	X																	
	Inflammatory conditions review	X										X ^C							
	Tumor specimen	X ^D										X ^E							
	saaIPI score or standard IPI score ^X	X																	
	Serology (hepatitis B) ^F	X																	
	Height		X																
	Electrocardiogram		X									X							
Pregnancy test for FOCP		X									X								
Treatment	Study treatment administration					X ^{G,Y}													
Blood-based PK/Biomarker/ ATA	PK				Refer to Sections 7.3 and 7.4, and Table 3														
	ATA																		
Response Assessments	Biomarker samples	X																	
	CT (chest, neck, abdomen, pelvis) ^H	X										X ^I		X	X	X	X	X	X
	PET ^H	X										X ^I		X ^J	X ^J	X ^J	X ^J	X ^J	X ^J
	BM biopsy results ^K	X ^K										X ^K							
Safety Assessments	B symptoms		X			X ^L						X							
	Survival status														X	X	X	X	X
	Physical exam with weight		X			X ^L						X ^Z		X ^Z	X ^Z	X ^Z	X ^Z	X ^Z	X ^Z
	Vital signs (Section 7.7.2)					X													
	ECOG (Appendix B)		X			X ^L						X							
	Serum chemistry (Section 7.7.3)		X ^{AA}			X ^M		X	X			X							
	Hgb A1c		X																
	CBC with differential		X			X ^M		X	X			X							
	PT/PTT/INR		X			X ^M						X							
	Spot urine for UPC ratio (Section 7.7.3)		X			X ^M		X	X			X							
	24-hr urine collection if UPC>2					X ^{M,N}		X ^N	X ^N			X ^O							
	Ophthalmology exam (Section 7.7.5)	X							X ^{L,P}			X ^{Q,R}	X ^S	X ^R	X ^R	X ^R	X ^R	X ^R	X ^R
	Ocular health survey ^T (Section 7.6.1)	X							X ^L			X ^{Q,R}	X ^S	X ^R	X ^R	X ^R	X ^R	X ^R	X ^R
	Con meds & AEs	Collect any related to study procedures				Collect from Day 1 (predose) thru 30 days post last dose							X ^U						
	Collect PBSC mobilization info (Section 6.5)				At time of PBSC collection								Collection of PBSC mobilization outcome. Refer to Section 6.7.						

- A Cycles 2 and 3 should not begin until adequate recovery of peripheral blood counts (i.e., platelets ≥75,000/μL and ANC ≥1000/μL). A delay of >7 days is discouraged
- B Perform EOT evaluations before initiation of non-protocol therapy. If EOT visit is <30 days after completion of study treatment, conduct a phone screen 30–37 days after completion of study treatment to ensure no change in AE profile has occurred
- C Required for patients with inflammatory conditions of interest at Screening (Section 7.1)
- D For screening (Section 7.1) and biomarker analysis (Section 7.4.4) Representative tissue from the most recent biopsy after the last therapy must be available; if such tissue is not available, a fresh biopsy must be obtained
- E For patients discontinuing treatment due to PD: if a tumor biopsy was performed at the time of disease progression as part of standard of care, submit sample of tumor specimen, if available
- F If positive, PCR for hepatitis B viremia must also be performed (Section 5.5.1)

- J Required until disease is PET negative
- K Results collected at screening and/or EOT visit and at any time on study, if performed as part of standard of care (Section 7.2)
- L Not required at Cycle 1
- M If baseline activities occur within 1 day prior to Cycle 1 Day 1, assessment does not need to be repeated
- N Prior to next cycle dosing, or prior to EOT visit if discontinuing study treatment
- O Within 5 days after UPC assessment
- P Window Day 14 to 21
- Q Not required if an exam was performed within 4 weeks prior to the EOT visit, and following the last dose of study treatment
- R In the event of ocular toxicity, continue at least monthly in follow-up until resolution or return to baseline
- S Ophthalmology exam and ocular health survey approximately 30-days post ASCT
- T ±2 days from the ophthalmology exam

- G For 19A+RICE Arm: Steroid eye drop prophylaxis should begin 1 day prior to denintuzumab mafodotin dose. See Section 5.4.1 and Table 1 for additional prophylactic interventions including artificial tears, vasoconstrictor eye drops, and cooling eye mask to be given at the time of infusion.
- H A combined CT/PET may be obtained to satisfy the requirements for CT and PET scanning, as long as the CT is of diagnostic quality (i.e., contrast-enhanced with IV and oral contrast, unless contrast is medically contraindicated). Images should be submitted for central review.
- I Unless PD is documented within the previous 6 weeks by diagnostic CT scan.
- U In each treatment arm, additional transplant-related data will be collected following ASCT until time of engraftment and will include, but not be limited to, the time to neutrophil and platelet engraftment.
- V Cycle 1 only. Blood samples for PK and biomarker testing (Table 3).
- W Cycle 1 and Cycle 2 only. Only for patients not continuing on treatment or not starting the next cycle on Day 22. Blood sample for PK testing (Table 3).
- X saAPI for patients aged ≤ 60 years, and standard IPI for patients aged >60 years (Appendix D).
- Y For both treatment arms, RICE administration to occur on Days 1–3 (± 1 day).
- Z Weight not required.
- AA Fasting blood glucose at baseline.

APPENDIX B: PERFORMANCE STATUS SCALES CONVERSION

Karnofsky		ECOG	
Percent	Description	Score	Description
100	Normal, no complaints, no evidence of disease.	0	Normal activity. Fully active, able to carry on all pre-disease performance without restriction.
90	Able to carry on normal activity; minor signs or symptoms of disease.		
80	Normal activity with effort; some signs or symptoms of disease.	1	Symptoms, but ambulatory. Restricted in physically strenuous activity, but ambulatory and able to carry out work of a light or sedentary nature (e.g., light housework, office work).
70	Cares for self, unable to carry on normal activity or to do active work.		
60	Requires occasional assistance, but is able to care for most of his/her needs.	2	In bed <50% of the time. Ambulatory and capable of all self-care, but unable to carry out any work activities. Up and about more than 50% of waking hours.
50	Requires considerable assistance and frequent medical care.		
40	Disabled, requires special care and assistance.	3	In bed >50% of the time. Capable of only limited self-care, confined to bed or chair more than 50% of waking hours.
30	Severely disabled, hospitalization indicated. Death not imminent.		
20	Very sick, hospitalization indicated. Death not imminent.	4	100% bedridden. Completely disabled. Cannot carry on any self-care. Totally confined to bed or chair.
10	Moribund, fatal processes progressing rapidly.		
0	Dead.	5	Dead.

APPENDIX C: NEW YORK HEART ASSOCIATION CLASSIFICATION

A Functional and Therapeutic Classification for Prescription of Physical Activity for Cardiac Patients

- Class I: patients with no limitation of activities; they suffer no symptoms from ordinary activities.
- Class II: patients with slight, mild limitation of activity; they are comfortable with rest or with mild exertion.
- Class III: patients with marked limitation of activity; they are comfortable only at rest.
- Class IV: patients who should be at complete rest, confined to bed or chair; any physical activity brings on discomfort and symptoms occur at rest.

On-line source: http://www.heart.org/HEARTORG/Conditions/HeartFailure/AboutHeartFailure/Classes-of-Heart-Failure_UCM_306328_Article.jsp

APPENDIX D: SECOND-LINE AGE-ADJUSTED INTERNATIONAL PROGNOSTIC INDEX (IPI) SCORE AND STANDARD IPI SCORE FOR NHL

saalIPI Score for Patients Aged ≤60 Years

Risk Factor	Score	
	0 point	1 point
Serum LDH	≤1 x ULN	>1 x ULN
ECOG Performance Status	0 or 1	2, 3, or 4
Stage	I or II	III or IV

LDH = lactate dehydrogenase

ECOG = Eastern Cooperative Oncology Group

ULN = upper limit of normal

Risk Category

Low	0
Low-intermediate	1
High-intermediate	2
High	3

Based on ([Hamlin 2003](#); [Moskowitz 1999](#); [Shipp 1993](#)).

Standard IPI Score for Patients Aged >60 Years

Risk Factor	Score	
	0 point	1 point
Age	≤60 years	>60 years
Serum LDH	≤1 x ULN	>1 x ULN
ECOG Performance Status	0 or 1	2, 3, or 4
Stage	I or II	III or IV
Extranodal involvement	≤1 site	>1 site

LDH = lactate dehydrogenase

ECOG = Eastern Cooperative Oncology Group

ULN = upper limit of normal

Risk Category

Low	0, 1
Low-intermediate	2
High-intermediate	3
High	4, 5

APPENDIX E: MODIFIED* CTCAE V4.03 GRADING SCHEME FOR OCULAR TOXICITY

Adverse Event	Grade 1	Grade 2	Grade 3	Grade 4
Ocular Symptoms	Symptomatic (with or without clinical findings) Does not affect ADL	Symptomatic Possible change in vision Affects instrumental ADL (i.e., preparing meals, shopping for groceries or clothes, using the telephone or computer, managing money, driving, etc.)	Symptomatic Change in vision Affects self-care ADL (i.e., bathing, dressing and undressing, feeding self, using the toilet, taking medications, and not bedridden)	--
Corneal Findings (as determined by ocular examination)	Corneal findings, but no change in visual acuity from baseline	Corneal findings with change in visual acuity from baseline; see table below for visual acuity criteria	Corneal findings with change in visual acuity from baseline; see table below for visual acuity criteria	Corneal findings with change in visual acuity from baseline; see table below for visual acuity criteria

ADL=activities of daily living

* Modified portion of CTCAE refers to when patient does not have 20/20 vision at baseline

Visual acuity for grading

Baseline Vision (cc or sc)	Grade 1	Grade 2	Grade 3	Grade 4
20/20	No change	20/25 – 20/40 or better	20/50 – better than 20/200	20/200 or worse
20/25	No change	20/30 – 20/50	20/60 – better than 20/200	20/200 or worse
20/30	No change	20/40 – 20/60	20/70 – better than 20/200	20/200 or worse
20/40	No change	20/50 – 20/70	20/80 – better than 20/200	20/200 or worse
20/50	No change	20/60 – 20/80	20/100 – 20/200	Worse than 20/400
20/60	No change	20/70 – 20/100	20/125 – 20/400	Worse than 20/400
20/70	No change	20/80 – 20/125	20/200 – 20/400	Worse than 20/400
20/80	No change	20/100 – 20/200	20/400	Worse than 20/400
20/100	No change	20/125 – 20/400	Worse than 20/400	--

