5.8.1 Dose Modifications for Ocular Events

Ocular adverse events are assessed as either ocular symptoms or corneal changes observed on ocular examination and are graded according to a modified CTCAE version 4.03 scheme (see [Appendix E](#)). [Table 2](#) describes the recommended evaluations, treatment, and dose modifications for denintuzumab mafodotin -associated ocular toxicity.

Per-patient dose delays and/or reductions of denintuzumab mafodotin are permitted in the event of Grade 3 ocular symptoms or Grade 4 corneal changes. Denintuzumab mafodotin dosing should be held until ocular symptoms recover to \leq Grade 2 or corneal changes recover to \leq Grade 3. The more conservative evaluation, treatment, and dose modification should apply in cases of simultaneous ocular symptom and corneal change toxicities. Dose modifications must be discussed with the medical monitor; deviations from the recommended dose modifications must be approved by the medical monitor.

In the event of ocular symptoms (i.e., dry eyes), the use of preservative-free artificial tears may be increased up to every 2 hours, as needed.

Steroid eye drops administered for the treatment of \geq Grade 2 ocular symptoms or \geq Grade 1 corneal changes should contain prednisolone 1% (or equivalent). The frequency and duration of steroid eye drop administration for the treatment of ocular toxicity is per the discretion of the treating physician. However, it is recommended that the initial frequency should be at least 6 times per day. Treatment can be supplemented with topical steroid ointment applied overnight depending on severity.

See Section [7.7.5](#) for additional details of the ocular safety monitoring plan. Refer to Section [7.7.1.2](#) and [Appendix E](#) for information regarding the grading of ocular events related to the cornea.

Table 2: Evaluation, treatment, and dose modifications in the event of ocular toxicity

CTCAE ^a	Evaluation and Treatment	Dose Modifications ^b
Ocular Symptoms		
Grade 1	Use of preservative-free artificial tears may be increased up to every 2 hours, as needed	Continue treatment with denintuzumab mafodotin without interruption or dose reduction.

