7.7.5 Ocular Monitoring Plan

In order to assess the effects of denintuzumab mafodotin on the eye, patients in both study arms will have complete ophthalmology assessments at protocol-defined timepoints (see Section 6 and [Appendix A](#)). Ophthalmology assessments are to include, but are not limited to, visual acuity and slit lamp examination. A baseline dilated fundus examination is required; subsequent dilated fundus examinations are to be conducted as clinically indicated. In particular, corneal epithelium changes must be assessed at each timepoint. Assessments must also include evaluation of steroid eye drop-induced changes including, but not limited to, intraocular pressure measurements and subcapsular cataracts. In addition, ophthalmologic evaluations will be obtained in the event of subjective visual or ocular disturbances while on study.

The results of the ophthalmological exam should be reviewed prior to the next dosing of denintuzumab mafodotin, and dose modifications of denintuzumab mafodotin should be made based on ocular toxicity grading of symptoms or corneal changes (see Section 5.8.1 and [Appendix E](#)) following discussion with the medical monitor.

Ophthalmology exams and ocular health surveys are required at baseline, the end of Cycles 2 and 3 (Days 15–21), EOT, and approximately 30-days post ASCT (for those patients who proceed to ASCT). In the event of ocular toxicity, ophthalmology exams should be conducted at least monthly during the follow-up period (unless discussed with the medical monitor) until resolution or return to baseline.

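### Appendix E gives no corneal grade for a patient with baseline vision 20/50 whose acuity is worse than 20/200 through 20/400, so neither the hold nor the resume rule is defined there

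*Protocol*

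**What the plan says.** Appendix E of the protocol defines corneal Grades 2 to 4 by reference to an acuity table: "Corneal findings with change in visual acuity from baseline; see table below for visual acuity criteria". In the baseline 20/50 row of that table, the cells for Grades 2, 3 and 4 are "20/60 – 20/80 20/100 – 20/200 Worse than 20/400".

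The grade feeds the dosing rule. Protocol 7.7.5 states that "dose modifications of denintuzumab mafodotin should be made based on ocular toxicity grading of symptoms or corneal changes". Section 5.8.1 makes dose delays or reductions "permitted in the event of Grade 3 ocular symptoms or Grade 4 corneal changes", and Table 2 turns this into actions for corneal changes: continue at Grades 1 to 3, hold at Grade 4. A held patient may resume if the change recovers to Grade 3 or lower within 7 days of the start of the current RICE cycle; otherwise that cycle's dose is skipped. Section 5.8.1 presents Table 2 as one that "describes the recommended evaluations, treatment, and dose modifications", and departures from it need the medical monitor's approval.

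On timing, 7.7.5 says "Ophthalmology exams and ocular health surveys are required at baseline, the end of Cycles 2 and 3", and the Appendix A footnote on the on-treatment eye exam reads "Not required at Cycle 1".

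On reporting, SAP 7.6.1.1 names ocular AEs as the events of special importance. SAP 7.6.1.1.1 tabulates them by maximum severity and defines improvement from the worst grade.

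**The concern.** The missing band lies on the only corneal boundary that changes dosing. A patient with corneal findings whose vision falls from 20/50 to 20/400 has lost a great deal of sight, and the protocol does not say whether the next dose should be held. A site that borrows from the row above would hold; one that borrows from the row below would continue. The continue reading gives the site nothing in Table 2 that prompts a call to the medical monitor.

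The same gap affects recovery. If a patient with baseline 20/50 is already on hold and improves to 20/400, nobody can say whether the change is now Grade 3 or lower, so resuming or skipping is equally undefined.

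In the analysis, such an event has no defined place in the maximum-severity table and no defined starting grade for the improvement rule.

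Baseline 20/50 is an eligible value: the monocular-vision exclusion in Section 4.2 is set at 20/200.

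**Working it through.** There is no stated figure to reproduce, so the check reads the table as bands and looks for acuities that fall in none.

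**Step 1: the row and its neighbours (Appendix E).**

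| Baseline | Grade 2 | Grade 3 | Grade 4 |
|---|---|---|---|
| 20/40 | 20/50 to 20/70 | 20/80 to better than 20/200 | 20/200 or worse |
| 20/50 | 20/60 to 20/80 | 20/100 to 20/200 | worse than 20/400 |
| 20/60 | 20/70 to 20/100 | 20/125 to 20/400 | worse than 20/400 |

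In the 20/40 row, Grades 3 and 4 meet at 20/200. In the 20/60 row they meet at 20/400. The 20/50 row takes its Grade 3 limit from around the first and its Grade 4 limit from the second.

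**Step 2: individual acuities for baseline 20/50.** 20/200 is Grade 3. 20/250, 20/300, 20/320 and 20/400 match no grade. 20/500 is Grade 4.

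**Step 3: all rows, on the levels the table prints.** The table uses 13 levels: 20/20, 25, 30, 40, 50, 60, 70, 80, 100, 125, 200, 400, and worse than 20/400. Pairs of a baseline and a worse level over the nine rows: 12+11+10+9+8+7+6+5+4 = 72. Of these, 71 map to exactly one grade. The exception is 20/50 to 20/400.

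The grade at 20/400, by baseline from 20/20 to 20/100, is 4, 4, 4, 4, none, 3, 3, 3, 2. Under Table 2 that is hold in four rows, continue in four and undefined in one. The undefined row is exactly where the action switches, so the pattern does not settle it.

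**Step 4: between printed levels.** Testing intermediate acuities as well (20/150, 20/160, 20/250, 20/300, 20/320) finds two more gaps, both between Grades 2 and 3: the 20/70 row between 20/125 and 20/200, and the 20/80 row between 20/200 and 20/400. Both sides of each gap mean continue, so they can leave an AE grade unclear but do not affect a hold. The count of 1 in 72 covers printed levels only.

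**Step 5: possible repairs to the 20/50 row.**

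| Repair | 20/200 | 20/250 to 20/400 | 20/500 |
|---|---|---|---|
| Grade 4 = worse than 20/200 | 3, continue | 4, hold | 4, hold |
| Grade 3 extended to 20/400 | 3, continue | 3, continue | 4, hold |
| Grade 4 = 20/200 or worse | 4, hold | 4, hold | 4, hold |

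All three close the gap. The third also changes the grade at 20/200, which the row already defines. The first two change only the undefined band, and either keeps the grade at 20/400 from rising as baseline worsens. The SAP improvement rule treats worst Grades 3 and 4 alike, so choosing between the first two changes dosing and the maximum-severity table but not the improvement rule.

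**The case against.** The best case against is that little depends on this. Table 2 is a recommendation, dose modifications go through the medical monitor, Grade 3 symptoms trigger their own hold, and 5.8.1 applies the more conservative action when symptoms and corneal changes coincide. Visual disturbance calls for an ophthalmology evaluation (7.7.5), and study drug may be stopped for an AE or by investigator decision (4.3.1). Only the Cycle 3 dose, one of three, follows a scheduled on-treatment eye exam. All of this stands and limits the risk. None of it assigns a corneal grade. The symptom hold also needs Grade 3, meaning an effect on self-care; loss that affects driving or computer use is Grade 2, at which Table 2 continues.

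Three stronger or different readings are tempting, and the documents do not support them.

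- A reader might infer that the 20/100 row is also wrong, because it runs "20/125 – 20/400 Worse than 20/400" for Grades 2 and 3 and shows a dash for Grade 4, so no corneal hold can be reached from that baseline. The dash looks deliberate: Appendix E uses the same symbol for the non-existent Grade 4 of ocular symptoms, and Grade 3 already takes the last acuity category.
- A reader might infer that the resume rule is safe, because an ungraded acuity has not been shown to be Grade 3 or lower, so the dose is skipped. By the same logic it has not been shown to be Grade 4, so no hold would start. Both are undefined.
- A reader might infer that this is the table's only gap. That is true of the Grade 3/4 boundary and of the printed levels, but not between printed levels (Step 4).

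**Conclusion.** The 20/50 row is wrong as written. It leaves acuity worse than 20/200 through 20/400 without a corneal grade, at the threshold where Table 2 moves from continue to hold, and nothing else in the protocol or SAP supplies one. Hold entry, resumption and the severity grade to report are all undefined in that band.

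The practical size is small. A patient must start at 20/50, develop corneal findings, fall into this band and not already be held for Grade 3 symptoms. The documents give no baseline acuity distribution, so the number affected is unknown and probably low. They do not show that any patient would be dosed unsafely. The complete remission analysis is not affected.

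The conclusion assumes that the row is printed as it appears in the extracted text. All its cells are present and the neighbouring rows read normally, so damage is unlikely, but a misread digit should be excluded by looking at the PDF page.

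**What to change.** In the baseline 20/50 row of Appendix E, change the Grade 4 cell to worse than 20/200 and leave Grade 3 at 20/100 to 20/200. This is the more cautious of the two repairs that touch only the undefined band. If the ophthalmology lead confirms that Grade 3 was meant to run to 20/400, as in the 20/60 row, extend Grade 3 instead and leave Grade 4 as it is. Table 2 needs no change.

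Notify sites, and before database lock regrade affected corneal events from the visual acuity results already collected.

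Ask the ophthalmology lead whether the dash in the 20/100 row is intended. Treat that as a query and do not rewrite the row by default. The Grade 2/3 gaps in the 20/70 and 20/80 rows remain after this change; they do not affect dosing.

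The cost is one table cell, a site notice and a small regrading exercise. On the printed levels the change affects 1 of 72 pairs, from no grade to Grade 4, and so adds one defined hold. The downside is possibly a few extra held or skipped denintuzumab mafodotin doses; each skipped dose is one of the three planned for that patient.

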APPENDIX F: RESPONSE ASSESSMENT – THE LUGANO CLASSIFICATION

Response and Site	PET-CT–Based Response	CT-Based Response
Complete Response	Complete metabolic response	Complete radiologic response (all of the following)
Lymph nodes and extralymphatic sites	Score 1, 2, or 3 ^a with or without a residual mass on 5PS ^b It is recognized that in Waldeyer's ring or extranodal sites with high physiologic uptake or with activation within spleen or marrow (e.g., with chemotherapy or myeloid colony-stimulating factors), uptake may be greater than normal mediastinum and/or liver. In this circumstance, complete metabolic response may be inferred if uptake at sites of initial involvement is no greater than surrounding normal tissue even if the tissue has high physiologic uptake	Target nodes/nodal masses must regress to ≤ 1.5 cm in LDi No extralymphatic sites of disease
Nonmeasured lesion	Not applicable	Absent
Organ enlargement	Not applicable	Regress to normal
New lesions	None	None
Bone marrow	No evidence of FDG-avid disease in marrow	Normal by morphology; if indeterminate, IHC negative
Partial Response	Partial metabolic response	Partial remission (all of the following)
Lymph nodes and extralymphatic sites	Score 4 or 5 ^b with reduced uptake compared with baseline and residual mass(es) of any size At interim, these findings suggest responding disease At end of treatment, these findings indicate residual disease	$\geq 50\%$ decrease in SPD of up to 6 target measurable nodes and extranodal sites When a lesion is too small to measure on CT, assign 5 mm \times 5 mm as the default value When no longer visible, 0 \times 0 mm For a node >5 mm \times 5 mm, but smaller than normal, use actual measurement for calculation
Nonmeasured lesion	Not applicable	Absent/normal, regressed, but no increase
Organ enlargement	Not applicable	Spleen must have regressed by $>50\%$ in length beyond normal
New lesions	None	None
Bone marrow	Residual uptake higher than uptake in normal marrow but reduced compared with baseline (diffuse uptake compatible with reactive changes from chemotherapy allowed). If there are persistent focal changes in the marrow in the context of a nodal response, consideration should be given to further evaluation with MRI or biopsy or an interval scan	Not applicable
No Response or Stable Disease	No metabolic response	Stable disease
Target nodes/nodal masses, extranodal lesions	Score 4 or 5 with no significant change in FDG uptake from baseline at interim or end of treatment	$<50\%$ decrease from baseline in SPD of up to 6 dominant, measurable nodes and extranodal sites; no criteria for progressive disease are met
Nonmeasured lesion	Not applicable	No increase consistent with progression
Organ enlargement	Not applicable	No increase consistent with progression
New lesions	None	None
Bone marrow	No change from baseline	Not applicable

Response and Site	PET-CT–Based Response	CT-Based Response
Complete Response	Complete metabolic response	Complete radiologic response (all of the following)
Progressive Disease	Progressive metabolic disease	Progressive disease requires at least 1 of the following
Individual target nodes/nodal masses Extranodal lesions	Score 4 or 5 with an increase in intensity of uptake from baseline and/or New FDG-avid foci consistent with lymphoma at interim or EOT assessment	PPD progression An individual node/lesion must be abnormal with: LDi >1.5 cm, and Increase by $\geq 50\%$ from PPD nadir, and An increase in LDi or SDi from nadir 0.5 cm for lesions ≤ 2 cm 1.0 cm for lesions > 2 cm In the setting of splenomegaly, the splenic length must increase by $> 50\%$ of the extent of its prior increase beyond baseline (e.g., a 15-cm spleen must increase to > 16 cm). If no prior splenomegaly, must increase by at least 2 cm from baseline New or recurrent splenomegaly
Nonmeasured lesion	None	New or clear progression of preexisting nonmeasured lesions
New lesions	New FDG-avid foci consistent with lymphoma rather than another etiology (e.g., infection, inflammation). If uncertain regarding etiology of new lesions, biopsy or interval scan may be considered	Regrowth of previously resolved lesions A new node > 1.5 cm in any axis A new extranodal site > 1.0 cm in any axis; if < 1.0 cm in any axis, its presence must be unequivocal and must be attributable to lymphoma Assessable disease of any size unequivocally attributable to lymphoma
Bone marrow	New or recurrent FDG-avid foci	New or recurrent involvement

5PS=5-point scale, CT=computed tomography, FDG=fluorodeoxyglucose, IHC=immunohistochemistry, LDi=longest transverse diameter of a lesion, MRI=magnetic resonance imaging, PET=positron emission tomography, PPD=cross product of the LDi and perpendicular diameter, SDi=shortest axis perpendicular to the LDi, SPD=sum of the product of the perpendicular diameters for multiple lesions.

- a A score of 3 in many patients indicates a good prognosis with standard treatment, especially if at the time of an interim scan. However, in trials involving PET where de-escalation is investigated, it may be preferable to consider a score of 3 as inadequate response (to avoid undertreatment). Measured dominant lesions: Up to 6 of the largest dominant nodes, nodal masses, and extranodal lesions selected to be clearly measurable in two diameters. Nodes should preferably be from disparate regions of the body and should include, where applicable, mediastinal and retroperitoneal areas. Non-nodal lesions include those in solid organs (e.g., liver, spleen, kidneys, lungs), gastrointestinal involvement, cutaneous lesions, or those noted on palpation. Nonmeasured lesions: Any disease not selected as measured, dominant disease and truly assessable disease should be considered not measured. These sites include any nodes, nodal masses, and extranodal sites not selected as dominant or measurable or that do not meet the requirements for measurability but are still considered abnormal, as well as truly assessable disease, which is any site of suspected disease that would be difficult to follow quantitatively with measurement, including pleural effusions, ascites, bone lesions, leptomeningeal disease, abdominal masses, and other lesions that cannot be confirmed and followed by imaging. In Waldeyer's ring or in extranodal sites (e.g., gastrointestinal tract, liver, bone marrow), FDG uptake may be greater than in the mediastinum with complete metabolic response, but should be no higher than surrounding normal physiologic uptake (e.g., with marrow activation as a result of chemotherapy or myeloid growth factors).
- b PET 5PS: 1, no uptake above background; 2, uptake \leq mediastinum; 3, uptake $>$ mediastinum but \leq liver; 4, uptake moderately $>$ liver; 5, uptake markedly higher than liver and/or new lesions; X, new areas of uptake unlikely to be related to lymphoma ([Barrington 2014](#)).

From: ([Cheson 2014](#))

